threatening, advanced, or recurrent; or the participant could have a history of a cancer diagnosis and currently be in remission or considered ‘cured’ as long as they continue to have anxiety related to the historical diagnosis of cancer. Subject’s life expectancy of approximately 6 months or more will be verified by the study’s oncologist [name] through the review of medical records. However, it is expected that some subjects will not complete the study due to rapid progression of their pre-existing diagnosis of cancer or death due to cancer.

Patients with epilepsy, renal disease, diabetes, abnormal liver function, severe cardiovascular disease (i.e. coronary artery disease, congestive heart failure) and uncontrolled hypertension will be excluded from the study. Subjects with a history of migraine headaches may be excluded based on severity of the migraines per evaluation of the principal investigator.

Cardiovascular screening: There will be at least four blood pressure assessment occasions over at least two separate days. Within a day, assessment occasions will be separated by at least 15 minutes. Each assessment occasion will involve two or more blood pressure readings. To qualify for the study, the mean blood pressure (mm Hg) of the four or more assessment occasions will not exceed 140 systolic and 90 diastolic.

Blood pressure will be measured while subjects are at rest and have been seated or supine for at least 5 minutes. As recommended by the Joint National Committee on Prevention, Detection, Evaluation and Treatment of High Blood Pressure, these assessments will involve the average of 2 or more readings separated by two minutes. If the first 2 readings differ by more than 5 mm Hg, additional readings will be obtained and averaged. On one or more of the blood pressure measurement occasions, the subject will be acclimated to the automated blood pressure monitoring equipment by repeatedly having blood pressure measured (at least 3 readings) with the device. It has been our experience that time-to-time blood pressure readings with the automated equipment can be variable due to measurement artifact, therefore any reading that initially exceeds the protocol’s threshold value will be reassessed twice within 4 minutes to assure accuracy.

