In the first six weeks following the experimental treatment sessions, several follow-up meetings (at least 3 for a total minimum of 6 hours) in person between the subject, the study staff and the monitors will be arranged to facilitate psychological integration of the psilocybin experience, as well as to administer the research measures. Additional meetings in person or on the telephone will be held at least monthly intervals for further follow-up for six months. The principal investigator will be the primary contact person for the subjects.

Communication with community observers (i.e. family members, friends, co-workers) will be part of follow-up as a way to get an objective measure of patient outcome in addition to self-report.

Drug Conditions

Psilocybin and niacin will be administered in identically appearing opaque, size 0 gelatin capsules with approximately 180ml of water. The dose of psilocybin will be 0.3mg/kg and the niacin dose will be 250mg. Each subject will participate in two experimental treatment sessions. In the study, approximately half of the subjects will be randomized to receive psilocybin (n=15 or 16) or the placebo, niacin (n=15 or 16). Following

the first treatment session of either the active agent or placebo, a cross-over design will be instituted with the alternative drug administered on the second session. Subjects and treatment personnel will be blinded for each experimental drug administration. The time interval between the two experimental treatment sessions will be 7 weeks (+ 1 week).

For both experimental treatment sessions, patients will be weighed as close as possible to the day before the session, and the dose of psilocybin will be mixed and compounded the day prior to the drug administration session at 0.3mg/kg (- 4 day window). Regarding niacin, it too will be mixed and compounded the day before the drug administration session (- 4 day window).

Justification for 0.3mg/kg dose of psilocybin

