- Participant LMN completed only 1 medication session but it was her active medication session. She withdrew from the study before her second medication session. However, since the protocol states that in order to be eligible for the optional & additional timepoints, participants must have only completed a psilocybin medication session, she would be eligible to participate in these additional and optional timepoints. If her consent endorsed having the study team reach out to her regarding future research, the study team will do so regarding these optional and additional questionnaire timepoints.

For documentation purposes, the study team will keep a log that includes all participants enrolled in the main portion of the trial and note whether or not they are deceased. Any and all information that the study team has regarding the death of a past participant in this trial will be noted.

Statistical Analyses (Including Power Analysis): Done in conjunction with [name] of Biostatistics and Approved on 1/24/07

Descriptive statistics (means, medians, standard deviations, frequency distributions) and graphic displays will be generated for demographics and baseline clinical presentations to characterize study subjects, and to describe the distribution of adverse events, patient dropout, study compliance and all outcome measures.

One of the objectives of this pilot study is to determine the feasibility of giving psilocybin to patients with advanced cancer. Although the safety of giving psilocybin to normal, healthy volunteers has been established within the last decade (Hasler 2004, Griffiths 2006, Moreno 1998), and although the safety of its use in patients with advanced cancer was established in the 1960s, it has not been established in patients with cancer using modern research designs (i.e. double-blind, placebo controlled, prospective methodology). In addition to safety determination considerations, summary statistics will be used to describe the consent and drop out rates as part of patient recruitment and retention. The adverse events associated with study treatments will be tabulated, and percent adverse event and its 95% confidence interval will be calculated.

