According to a recent study by Moreno and colleagues, published in 2006, in patients with refractory Obsessive Compulsive Disorder (OCD), an anxiety spectrum disorder, it was found that, with psilocybin, subject's mean YBOCS scores were reduced to 10.67 at 24 hours from 24.11 +/- 6.3 at baseline (Moreno 2006). This represents a reduction of 2 in effect size (assuming a 0.5 correlation between baseline and 24 hours). If we assume placebo has no effect on anxiety, depression and pain, a sample size of 16 subjects in each group (in the first treatment session) will provide 75% power to detect a reduction of 1 effect size, and > 99% power at 2 effect sizes, at the 5% level. This power analysis shows that even if patients dropout before the second cross-over session, the total of 31 patients in the first session will have adequate power for the study endpoints.

Regarding the effect of psilocybin on the outcome variables measuring anxiety, the STAI and HAD scale, analyses will be conducted using a paired t-test to evaluate the effect of treatment over time. The comparisons will be between the following time points: (T0 & T1)-T4, (T0 & T1)-T5, (T0 & T1)-T6, and (T0 & T1)-T7. The comparisons between the active agent and placebo groups will be conducted using an independent sample t-test to look at differences on the STAI and HAD scale measures. Similar analyses will be conducted both within and between groups for the other outcome measures, assessing for depression (POMS-SR, BSI and BDI scales) and pain (BPI-SF, MSAS, and MSKCC scales).

To assess the interaction between drug and time, a series of repeated measures multivariate analyses of variance (MANOVA) will be used to compare the active drug and placebo study arms across time in terms of the major outcome variables during the first and second randomized experimental treatment sessions. Both treatment main effects across time and interactions of treatment with time will be assessed in the repeated measures MANOVA.

Longer-term effects will be measured in two ways looking at the outcome measures of anxiety, depression, and pain. First the effect of time will be assessed with a MANOVA analysis from baseline relative to T7-T12. Also, MANOVA will be used to look at the effect of sequencing of getting the active agent vs. placebo in a sequence x time analysis from baseline relative to T7-T12.

Data Management and Statistics:

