Research with psilocybin has resumed within the last several years and has been safely given to normal volunteers, regarding physiological parameters, at doses ranging from 0.045mg/kg to 0.43mg/kg (Hasler et al. 2004; Griffiths et al. 2006). It has also been safely administered, again regarding physiological parameters, to patients with OCD at doses ranging from 0.025mg/kg to 0.3mg/kg (Moreno et al. 2006). Moreover, a completed double-blind, placebo-controlled (niacin as the control), Phase I study with a cross-over design at Harbor-UCLA Medical was conducted by [name], where patients with advanced cancer and anxiety received a single dose of 0.2mg/kg of psilocybin. In total, 12 out of 12 patients were enrolled and completed the study. As mentioned above, the study established the safety and feasibility of administering a moderate dose of psilocybin to patients with advanced cancer and anxiety. Some of the data suggested a treatment effect with reduction in anxiety and depressive symptoms (Grob 2010).

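### Longer-term effects (T7-T12) are tested only by MANOVA with no stated rule for missed visits; a mixed model on all available scores would cheaply recover part of the power that incomplete follow-up may cost

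*Combined protocol and SAP*

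**What the plan says.** The section Statistical Analyses (Including Power Analysis) gives longer-term effects two tests. For time: "First the effect of time will be assessed with a MANOVA analysis from baseline relative to T7-T12". For sequence: "MANOVA will be used to look at the effect of sequencing of getting the active agent vs. placebo in a sequence x time analysis", over the same window. The paired t-tests in that section stop at T7, so T8-T12 have no test other than MANOVA.

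The only power statement concerns the first treatment session, where 16 patients per group "will provide 75% power to detect a reduction of 1 effect size". Dropout enters that argument only to say that loss before the second session leaves the first-session comparison adequately powered. Otherwise dropout is to be summarised: descriptive statistics are planned "to describe the distribution of adverse events, patient dropout, study compliance and all outcome measures". The available text names no imputation, likelihood-based model or analysis set for incomplete follow-up.

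The eligibility section foresees loss: "it is expected that some subjects will not complete the study due to rapid progression" of the cancer, or death. It also admits lower-risk patients: "the participant could have a history of a cancer diagnosis and currently be in remission". Follow-up contact is frequent: "Additional meetings in person or on the telephone will be held at least monthly intervals for further follow-up for six months". Of the earlier cancer study the safety section reports: "In total, 12 out of 12 patients were enrolled and completed the study".

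**The concern.** A MANOVA over baseline and six later visits needs all seven scores from each patient. Unless the plan says otherwise, standard software drops anyone with a gap. A patient seen at five of the six visits then contributes nothing, and the error degrees of freedom, already few with 31 patients, fall with each exclusion.

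This matters because lasting benefit is part of the stated hypothesis, and Objectives and Purpose of the Study plans to analyse six months of data after the second session for all enrolled participants. If T7-T12 are counted from the second session, T12 falls 2-4 + 7-8 + 26 = 35-38 weeks after T0, while entry requires a life expectancy of only about six months. A moderate lasting change could be missed although many of the scores needed to show it had been collected. Loss through progression or death could also be related to anxiety, mood and pain, so an analysis of complete cases may describe the healthier patients.

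**Working it through.** **1. The plan's own power figure.** Two-sided two-sample t-test, 5% level, difference 1 SD, noncentrality √(n₁n₂/(n₁+n₂)):

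- 16/16: 2.828, power 78.1%
- 16/15: 2.782, power 76.7%
- 15/15: 2.739, power 75.3%

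The stated 75% is thus reproduced to within 2 points at 15/16 or 15/15. It describes the first session and says nothing about T7-T12.

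**2. Complete patients.** The documents give no loss rate. Under an assumed constant permanent loss per visit over six visits, the expected number complete is 31 × (1 − rate)⁶:

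- 2%: 31 × 0.886 = 27.5
- 5%: 31 × 0.735 = 22.8
- 10%: 31 × 0.531 = 16.5 (about 47% cumulative loss)

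**3. MANOVA power for time.** There are six contrasts, each of T7-T12 minus baseline, and two sequences. F has 6 and N − 7 degrees of freedom. The noncentrality is 4(n₁n₂/N) × δ² × q, where q = 1′Σ⁻¹1 and Σ is the covariance of the contrasts in SD units. Correlations are assumed; the plan gives 0.5 only for baseline against 24 hours in another study. With AR(1) 0.7, q = 1.793; with equal correlation 0.5, q = 6/3.5 = 1.714.

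| Complete N | Error df | 0.5 SD, AR(1) 0.7 | 0.5 SD, equal 0.5 | 1 SD, AR(1) 0.7 |
|---|---|---|---|---|
| 31 (16/15) | 24 | 68.4% | 66.1% | >99.9% |
| 23 (12/11) | 16 | 47.9% | 45.9% | 99.0% |
| 16 (8/8) | 9 | 26.8% | 25.7% | 84.4% |

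For example, at N = 31 and 0.5 SD with AR(1), the noncentrality is 4 × (16 × 15/31) × 0.25 × 1.793 = 13.88.

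**4. Mixed model against MANOVA.** These results are simulated: N = 31, saturated means, unstructured covariance, REML with Kenward-Roger F, permanent dropout completely at random from T7 on, 3,000-4,000 trials, error about ±2 points. The mixed-model critical value was reset to give a true 5% error. At 5% loss per visit:

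| Time effect | Correlation | Mixed model | MANOVA |
|---|---|---|---|
| 0.5 SD | AR(1) 0.7 | 62.0% | 48.8% |
| 0.5 SD | equal 0.5 | 57.9% | 46.8% |
| 1 SD | AR(1) 0.7 | 99.9% | 98.2% |
| 1 SD | equal 0.5 | 99.8% | 97.3% |

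At 2% loss (0.5 SD, AR(1) 0.7) the figures are 66.6% and 62.5%. With complete data the two tests coincide.

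**5. Precision.** With 20% permanent loss and known covariance, completers keep 80% of full precision. The mixed model keeps 86-90% at T12 and 94-96% for the T7-T12 average. The gain at T12 alone is therefore modest.

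**6. Error rate of the replacement.** Without resetting the critical value, the unstructured Kenward-Roger test had type I error of about 6% at 5% loss per visit and 8-9% at 10%; MANOVA had 4.4-5.5%. About 1% of fits failed to converge at 10% loss and none at 5%.

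**7. Sequence by time, for illustration only.** With a constant 1 SD difference and equal correlation 0.5, MANOVA power is 66.1% at N = 31 and 45.9% at N = 23. At 5% loss the simulated figures are 55.4% for the mixed model and 45.2% for MANOVA.

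**The case against.** The strongest reply is that little may be lost. This is a pilot powered on its first session, the loss rate is unknown, patients in remission may enter, contact is monthly and partly by telephone, and the earlier study kept all 12 patients. The 0.5 SD effect is our assumption; at the plan's 1 SD the time test barely suffers at 5% loss per visit. All of this stands. It limits the size of the point but does not supply the missing rule.

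Four further objections also stand:

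- **Sequence by time.** By T8-T12 both sequences have received psilocybin, so under the plan's hypothesis of lasting benefit any difference should shrink. A reader might take the figures in step 7 as realistic losses. They are not, because a constant 1 SD difference is not what the crossover predicts.
- **Heavy loss.** A reader might infer that an unstructured mixed model rescues the analysis at 10% loss per visit. Under a rule that switches to a simpler covariance when fewer than about 20 patients are complete, the switch would occur about 86% of the time (binomial, 31 patients, probability 0.531), and the power of that simpler model was not assessed.
- **Early loss.** If T7-T12 follow the second session, patients lost before it supply no later scores to either method. The simulation starts losses at T7 and so favours the mixed model.
- **Error control.** Where loss is random, MANOVA holds its level, and the unstructured mixed model is somewhat liberal.

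**Conclusion.** The concern holds as a cheap improvement to the longer-term analyses. T8-T12 are tested only by MANOVA, no rule for incomplete data is stated in the available text, and the protocol itself expects non-completion. Under an assumed 5% loss per visit, an assumed lasting 0.5 SD change, the assumed correlations and loss completely at random, MANOVA power falls by about 20 points (about 68% to 48%), and a mixed model at a true 5% error reaches about 58-62%. At 1 SD, MANOVA power stays near 98-99% (97% in the simulation with equal correlation).

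Two stronger readings go too far. A reader might infer that the plan orders incomplete patients to be discarded. It does not: that is what software does when the plan is silent. A reader might also infer that the longer-term analysis is invalid or badly underpowered. The documents support neither, since they give no loss rate and a large time effect survives moderate loss. Nor does a mixed model settle bias from progression or death: it assumes data missing at random and implicitly extrapolates scores past death.

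**What to change.** Replace the two T7-T12 MANOVAs with a mixed model for repeated measures on all available scores, with sequence, visit and sequence by visit, fitted by REML with Kenward-Roger degrees of freedom. In the same text:

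- Define the baseline as T0 and T1 scores taken before the first session only. T1 is scheduled before each session, so a second T1 follows psilocybin in about half the patients.
- State which session T7-T12 are counted from. Six weeks after the first session still precedes the crossover at 7-8 weeks, so the choice changes what sequence by visit means.
- Name the covariance in advance: unstructured, with a simpler structure such as AR(1) if the model does not converge or complete cases fall below a stated number (for example, about 20).
- State the missing-at-random assumption and how scores after death are treated.
- Break the planned dropout description down by visit, separating deaths from other loss.
- Add one sensitivity analysis, such as summaries among patients alive at each visit.

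Multiple imputation under the same assumption would be an acceptable alternative. The short-term t-tests need not change.

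The cost is analysis wording and standard software, with no new data. The price is the mild excess in type I error given above. Before the fallback is fixed, its power and error rate should be checked by simulation.

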It is hypothesized that a one time experience with psilocybin will occasion significant shifts in consciousness and awareness that will lead to short-term (i.e. hours to days) and long-term (up to 5 years in this study following the second experimental session) improvement in anxiety, depression, and pain associated with cancer. The exact mechanism of action is unclear but based on studies conducted with similar serotonergic agents in patients with advanced cancer, improvements in anxiety levels, mood and pain were reported (Grob and Halifax 1977; Kast 1970). However, a treatment model developed by the British psychiatrist, Humphrey Osmond, offers one possibility. In this model, serotonergic hallucinogens' therapeutic mechanism lies in their ability to allow the individual to access novel dimensions of consciousness and their efficacy or lack thereof relies on whether a significant reappraisal or alteration in perception is attained (Osmond 1957). Another possible mechanism relates to what Dobkin de Rios and Grob have described as 'managed altered states of consciousness,' where the power of suggestibility, occurring in a safe setting, allows one to transcend a particular state of consciousness (i.e. anxiety and depression associated with cancer) as a means to facilitate emotional discharge and to manage irreconcilable conflict (Dobkin de Rios, Grob, & Baker 2002).

Rationale and Background:

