This is a pilot study of a single treatment designed to preliminarily evaluate the effect of psilocybin in patients with cancer and anxiety. Secondary outcome measures will be pain perception, depression, and existential / psychospiritual distress. Also, issues related to the feasibility of using psilocybin in patients with cancer and anxiety will be described. The study will look at both short-term, immediate effects as well longer-term effects. We plan to collect and analyze data up to 6-months post the second drug administration for all enrolled participants. Participants who complete a psilocybin dosing session and agree to be contacted will be invited to partake in two optional data collection time points, which will look at long-term psychological effects of psilocybin-assisted psychotherapy.. Subjects’ participation in these two additional longitudinal timepoints will be optional and will not affect their previous study involvement as research participants. Study participants who opt out or who do not have the option to participate (for example, if they are deceased) will be classified (ie study completers, withdrawn, treatment dropout, etc.) as they were in the main portion of the study. Participants do not need to complete all questionnaires given at previous time points to be eligible to participate in optional time points T13 and T14.

Criteria for patient selection (Inclusion/Exclusion Criteria)

The proposed project will involve up to 47 subjects 18-76 years of age. Subjects will have a current or historical diagnosis of cancer with a projected life expectancy of approximately 6 months or more and a DSM-IV psychiatric diagnosis, as determined by the Structural Clinical Interview for DSM-IV (SCID), of one of the following Anxiety Disorders: Acute Stress Disorder, Generalized Anxiety Disorder, Anxiety Disorder Due to cancer, or Adjustment Disorder with Anxiety. The cancer could be: at any stage of active illness; potentially life

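### After crossover (T8-T12), neither planned longer-term analysis has a comparator unexposed to psilocybin, so neither can attribute lasting change to the drug

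*Combined protocol and SAP*

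**What the plan says.** The Hypothesis section predicts that one psilocybin experience will lead to "long-term (up to 5 years in this study following the second experimental session) improvement in anxiety", as well as in depression and pain.

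The Statistical Analyses section covers this as follows: "Longer-term effects will be measured in two ways looking at the outcome measures of anxiety, depression, and pain". The first way is: "First the effect of time will be assessed with a MANOVA analysis from baseline relative to T7-T12". It has no arm or treatment term. The second is "the effect of sequencing of getting the active agent vs. placebo in a sequence x time analysis from baseline relative to T7-T12". No other longer-term test is planned.

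On timing, Drug Conditions has every patient cross to the other agent ("The time interval between the two experimental treatment sessions will be 7 weeks (+ 1 week"). In the measurement schedule, T7 is 6 weeks, T8 is 10 weeks and T12 is 26 weeks after drug administration. The schedule does not say which of the two administrations these weeks are counted from. Objectives and Purpose speaks of a plan to "collect and analyze data up to 6-months post the second drug administration", which points to session 2 without saying so for T7-T12. The short-term tests take T0 and T1 together as baseline; the baseline of the longer-term MANOVAs is not defined.

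On the population, the selection criteria exclude patients scoring below 8 on the HAD at T0, and add that "it is expected that some subjects will not complete the study due to rapid progression" of their cancer, or death from it. All patients get at least 6 hours of preparation and at least 6 hours of follow-up meetings.

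**The concern.** The long-term hypothesis is about the drug, but the randomised comparison with niacin ends at session 2.

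- **Time effect.** With no unexposed group, it combines any drug benefit with regression to the mean after entry on a HAD cutoff, the supportive sessions given to everyone, natural course, and selective loss of patients who progress or die. The plan states no missing-data rule, and repeated-measures MANOVA by default drops any patient with a missing visit.
- **Sequence by time.** After crossover this compares two groups that differ only in when they had psilocybin. A null result does not count against a lasting effect, and a difference does not count for one.
- **T7.** If T7 is the visit 6 weeks after session 1, it precedes crossover and is a genuine drug-versus-niacin contrast. A significant test over T7-T12 could then come from T7 alone and be misread as an effect lasting to week 26.

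At stake is whether the trial's long-term findings are read as controlled evidence in either direction.

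**Working it through.** **The plan's own figure.** The section gives no figure for the longer-term analyses. Its only computed figure is first-session power: 75% at effect size 1 and above 99% at effect size 2, with 16 per group at the 5% level. A two-sided t-test gives 76.7% with 15 and 16 patients (the stated total of 31) and 78.1% with 16 and 16; at effect size 2, power exceeds 99.9%. So 75% is reproduced within 2 points at a total of 31. It does not bear on this point.

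**Step 1: timeline.** Session 2 falls at week 7 to 8.

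| Visit | Counted from session 1: weeks since session 2 | Counted from session 2: weeks since session 1 |
|---|---|---|
| T7 (6) | 6-8 to 6-7 = -2 to -1 (before crossover) | 6+7 to 6+8 = 13 to 14 |
| T8 (10) | 2 to 3 | 17 to 18 |
| T12 (26) | 18 to 19 | 33 to 34 |

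On either clock both sequences have had psilocybin by T8. On the session-2 clock this is already so at T7, and T12 is 26 weeks after psilocybin for niacin-first patients but 33 to 34 weeks for psilocybin-first.

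**Step 2: expected sequence contrast.** Assume psilocybin lowers a score by 1 SD with half-life h weeks, and session 2 is at week 7. On the session-1 clock, psilocybin-first minus niacin-first is -2^(-w/h) at T7 (w = 6) and -2^(-w/h) + 2^(-(w-7)/h) from T8.

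- Persistent effect: -1.0 at T7 and 0 at T8-T12.
- h = 26: -0.85 at T7; -0.77 + 0.92 = +0.16 at T8 (before rounding of the terms); +0.10 at T12.
- h = 8: -0.59 at T7; -0.42 + 0.77 = +0.35 at T8; +0.09 at T12.

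A waning benefit makes psilocybin-first look worse after crossover. On the session-2 clock the contrast is zero throughout if the effect persists, and positive throughout (for example +0.13 to +0.19 at T8) if it wanes.

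**Step 3: what each test responds to.** 4,000 simulated trials, 16 versus 15 patients, Hotelling T² on changes from baseline. Assumed, not in the documents: SD 1, within-patient correlation 0.5, no dropout.

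| Scenario | Time, T7-T12 | Sequence x time, T7-T12 | Sequence x time, T8-T12 |
|---|---|---|---|
| Persistent 1 SD drug effect, session-1 clock | 100% | 67% | 4.8% |
| No drug effect, 1 SD shared improvement | 100% | 4.4% | 4.3% |
| Persistent 1 SD drug effect, session-2 clock | 100% | 5.2% | 5.2% |

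The time test does not separate the first two rows. The 67% comes entirely from T7.

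**Step 4: one illustration of the shared shift, regression to the mean on the HAD.** Assumed: HAD mean 8 to 14 before selection, SD 4, retest correlation r 0.6 to 0.8 between any two visits, n = 31, no drug effect. The spurious improvement in SD units is (1-r) × E[Z | Z > (8-mean)/4] from T0, half of that from the T0/T1 average, and zero from T1.

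- Mean 8, r 0.6: 0.4 × 0.798 = 0.32.
- Mean 10, r 0.8: 0.2 × 0.509 = 0.10.

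Share of trials significant on a paired t-test at one follow-up visit (20,000 simulations):

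| Baseline | Mean 8-10 | Mean 12-14 |
|---|---|---|
| T0 | 14-54% | 6-12% |
| T0/T1 average | 8-21% | 5-7% |
| T1 | 5% | 5% |

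Hotelling T² on six follow-up changes, closer to the planned MANOVA, gives about 10-45% (T0) and 7-18% (T0/T1 average) at mean 8-10.

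**The case against.** The strongest defence has four parts.

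- **T7 may be randomised.** A reader might infer that no test over T7-T12 can carry any drug information. The documents do not support that. On the session-1 clock, sequence by time from baseline to T7 is a valid randomised contrast at 6 weeks. This stands, and it limits the point to T8-T12 unless the clock runs from session 2. Table 1, which may settle the clock, is not visible in the text reviewed.
- **Not everyone need be exposed.** A reader might infer that every patient has had psilocybin from T8. That is true by design only: the power paragraph foresees dropout before the second session, and niacin-first patients who leave then are never exposed. The plan does not say how they enter, and they are not a randomised control group.
- **The plan does not call these tests efficacy evidence.** It labels them effects of time and of sequencing, has separate between-group tests and a treatment-by-time MANOVA for the two sessions, and is a pilot. This is fair: misreading is a risk, not a stated intention. But these are the only longer-term tests, and the hypothesis they serve attributes lasting improvement to psilocybin.
- **The regression-to-the-mean figure is fragile.** The high values need T0 as sole baseline and a mean near the cutoff. Patients must also have a diagnosed anxiety disorder, so a higher mean is plausible. This stands, and the range must include 5%.

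**Conclusion.** The point holds for T8-T12. Among patients who stay on protocol there is no unexposed comparator on either clock, so the pooled time effect cannot separate drug from shared change, and sequence by time after crossover is zero for a persistent effect and reversed for a waning one. T7 counted from session 1 is the only drug-versus-niacin contrast in the range; counted from session 2, there is none. This follows from the design and needs no assumed figures.

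The simulated rejection rates depend on the assumed correlation and on no dropout. Selection on the HAD alone would make the time test significant in about 5-54% of trials, depending on the assumed mean and correlation and on which baseline is used. That range applies to the HAD only, not to the STAI, depression or pain scales, and the conclusion does not depend on it. A reader might infer that a spurious long-term finding is likely; the documents give no HAD distribution and no longer-term baseline to support that.

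This should be changed before the longer-term results are interpreted. It does not affect the comparison before session 2.

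**What to change.** 1. State which session T7-T12 are counted from, and define the longer-term baseline (T0, T1 or their average).
2. Limit drug-versus-niacin inference to visits before session 2, the last being T7 of session 1, and report that visit separately from later ones.
3. Analyse T8-T12 as uncontrolled within-patient change, with estimates and 95% confidence intervals, aligned on weeks since psilocybin. Use a mixed model on all available visits in place of repeated-measures MANOVA. This keeps patients with missing visits but does not by itself remove bias from loss through progression or death.
4. State how niacin-first patients who leave before session 2 are handled.
5. Do not use sequence by time after crossover as evidence for or against efficacy.
6. Give any T13 or T14 results the same uncontrolled label. The plan names no test for them, and only patients who completed a psilocybin session are eligible.

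The cost is analysis-plan wording and a different model on data already scheduled, with no extra patients or visits. The downside is that the long-term result cannot be claimed as controlled evidence.
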